Adherence to all medications will be evaluated by electronic monitors and self-report. Weeks on treatment will be determined by electronic monitors and chart review. HCV viral load, virological endpoints, and resistance results will be obtained by chart review and blood draw, if unavailable by chart review. IMB model mediators will be assessed at weeks 8 and 12. Potential moderators will be assessed at each monthly visit.

Table 3. Overview of Data Collection by Aims

Aim & Hypothesis	Construct	Measure, source	Research visit (week)	Source
Outcome Measures				
Aim 1, H1	Adherence	Med-ic® and MEMS® Electronic Monitors	4,8,12	Electronic
Aim 1, H2	Completion	Medical record	NA	Chart
Aim 1, H3	Viral load (SVR)	HCV VL by Roche TaqMAN assay	0,4,8,12, 24, FU 4, FU12, FU24	Chart, Blood
Aim 1/2, H4	Resistance	HCV GenoSURE NS3/4A, NS5A, NS5B (Monogram)	4, 8, 12, 24, FU4, FU12, FU24	Chart, Blood
Aim 3	Cost	HCV treatment mDOT and CGT interventions Non-HCV treatment health services	NA NA 12,24, FU4, FU12, FU24	Chart Logs, Direct Observation Q
Other covariate measures*				
All	Demographics	Age, race/ethnicity, education, income, housing	0	Q
All	HCV-related clinical information	HCV VL, HIV, HCV genotype/subtype, IL28B, APRI and FibroSURE (biomarkers of liver fibrosis)	0	Chart
All	Substance use	Addiction severity Index-Lite (ASI-lite) (152,153) Alcohol use (AUDIT) (154) Urine toxicology EMIT assay	0,4,8,12, 24, FU4, FU12, FU24	Q, Urine
All	Methadone dose opiate withdrawal	Methadone dose; Subjective and Objective Opiate Withdrawal Scales (SOWS and OOWS) (155)	0,4,8,12, 24, FU4, FU12, FU24	Q
All	Neuropsychiatric	MINI (138-140)	0	Q
All	Information, motivation, and behavioral Skills	Health Beliefs Model (161) HCV Motivation (161) Adherence Self-Efficacy (161)	0, 12	Q
All	Social support	Medical Outcomes Scale (162)	0,4,8,12,24, FU4, FU12, FU24	Q
All	DAA levels	GC-MS (if additional funding obtained)	4	Blood
All	Depression, anxiety, and hostility	Depressive symptoms (BDI-II) (156-157) Brief Symptom Inventory (BSI) anxiety subscale (158) BSI hostility subscale (158-160)	0,4,8,12,24, FU4, FU12, FU24	Q
All	Psychosocial factors	Stages of readiness for HCV treatment (183) Trust in physician (184)	0 0,4,8,12,24, FU4, FU12, FU24	Q
All	Quality of life	HCV QOL and EQ-5D (163-166)	0,4,12, 24, FU4, FU12, FU24	Q
All	Med side-effects	Adult ACTG adherence instrument – revised (167)	0,4,8,12, 24, FU4, FU12, FU24	Q

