All	Adherence (self report)	Adult ACTG adherence instrument (167) Visual Analogue Scale (VAS) (168) 24 hour dietary recall instrument	0,4,8,12,24	Q

Q=Questionnaire

*All measures used in [name] pilot K23 HCV DOT study or [name] current R01 study

D. 10.3. Definitions of outcome measures.

Med-ic® or MEMS® missed dose adherence. For DAA and ribavirin (if applicable), adherence will be calculated as Med-ic blister pack dose openings divided by total number of prescribed doses in time interval. For example, Med-ic adherence for one week would be X/7Y, where X=number of Med-ic dose openings recorded in one week and Y=number of doses prescribed per day.

HCV treatment completion. Subjects will be considered to have completed treatment if they have completed at least 80% of the planned treatment course (at least 10 weeks of 12 week course, or at least 20 weeks of 24 week course) based on response guided therapy approach.^{98,115}

Sustained viral response (SVR). SVR is defined as undetectable HCV viral load 12 weeks after treatment completion or discontinuation.

Resistance. Subjects will be considered to have new drug resistance if they have a telaprevir- associated mutation (any substitutions at V36, T54, R155, A156) at any time point during the study, and the specific mutation did not exist at baseline. Subjects will be considered to have new drug resistance if they have a ledipasvir- associated mutation (K24R, M28T/V, Q30E/H/K/L/R, L31V/M/I, and Y93H/N) during the study, and the specific mutation did not exist at baseline. Subjects will be considered to have new drug resistance if they have a sofosbuvir- associated mutation (S282T) at any time point during the study, and the specific mutation did not exist at baseline.

Cost. Costs of HCV treatment will be collected using the same methods as in the pilot analysis (see Section D.1.8 above), by conducting chart reviews and assigning unit costs to all provider visits, lab tests, and medications based on Medicare fee schedules. The cost of the mDOT intervention will be determined by conducting observational time studies of the additional medical provider and patient time required for mDOT,

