using prevailing national wage rates to determine the cost of the time, and applying this cost to each DOT interaction. Patient time costs will be valued based on the minimum wage, because most patients are likely to be unemployed. The cost of the CGT intervention will be similarly determined through observational studies, as well as staff member time and activity logs, and expense logs will be maintained for transportation and other incidental costs. Provider time spent on research activities, such as conducting research visit assessments, will be excluded. We will also examine the cost of health care services received outside of the study (emergency department visits, hospitalizations, substance abuse treatment) based on quarterly patient self-reports.

D.10.4. Data Sources. There will be 6 data sources. Results will not be provided to participants' medical providers unless participants specifically request (in writing) that study staff release this information.

Medical record. HCV viral load and resistance assays (if no SVR) will be obtained when possible by chart review. HCV viral load is measured by the Roche TaqMAN assay and HCV resistance is measured by the Monogram HCV GenoSURE NS3/4A assay, which is automatically run on any HCV viral load which is ≥ 2000 IU/ml. Information on treatment interruptions and discontinuation will be obtained from medical records.

Blood. Three tubes of blood will be drawn at weeks 0, and 4, and stored at Einstein's Clinical Research Center (CRC). HCV viral load and resistance assays will be performed if not available by chart review. For subjects who fail to achieve SVR, resistance testing will be performed on post-treatment specimen. All testing will be performed at Montefiore's laboratories.

Urine toxicology. Participants will provide urine specimens at each research visit, which will be tested for cocaine and opiates (and pH to ensure validity) using enzyme multiplied immunoassay technique.

Adherence by electronic monitors (Med-ic® and MEMS®) and self-report.

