D.11. Analytic plan. First, the success of randomization will be checked by comparing the mDOT, CGT and TAU groups on key variables, such as age, gender, ethnicity, race, HCV viral load, HCV subtype (1a vs. 1b), BMI, psychiatric history, active drug use, and social support.⁴⁶ By design, IL28B and stage of liver disease will be represented equally in each arm. Continuous variables will be compared between arms using the ANOVA or Kruskal-Wallis test, and categorical variables will be compared using chi-square or Fisher's exact tests. Variables that are not equally distributed will be included in multivariate models. In primary analysis, we will use the intention-to-treat principle, which preserves the advantages of a randomized design.

D.12.1. Hypotheses for Aim 1. We hypothesize that in the intensive intervention arms, compared to the control arm, rates of adherence, treatment completion, and SVR will be significantly higher, and that rates of resistance will be lower. We further hypothesize that the proportion of subjects in the intensive models of care arms who achieve an SVR will be equivalent to that observed in large registration trials.

D.12.2. Analytic plan for Aim 1. Adherence to DAAs, ribavirin, and IFN will be determined using electronic monitors and self report, as described above. Initially, adherence will be calculated as a single outcome for each subject, evaluated at the end of the study. We will use Chi-square tests or Fisher's exact test to compare the proportion of subjects who achieve high adherence rate ($\geq 80\%$) complete treatment, achieve SVR, and develop resistance in the three arms (mDOT, CGT, and TAU). If the omnibus equality test of adherence across the 3 groups is rejected, we will conduct the following 2 specific post-hoc pairwise tests with a Bonferroni adjusted 2-sided alpha= 0.025: mDOT vs. control, and CGT vs. control. This strategy will be applied to multivariable logistic regressions if any potential confounding variables not equally distributed between the study arms at baseline are identified.

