D.12.4. Analytic plan for Aim 2. The proportion of participants (n=150) who develop resistance will be determined with 95% confidence interval (CIs) calculated using exact binomial methods. The proportion of participants with resistance will then be determined within each of 4 groups determined by quartiles of adherence measured at the final time point in the study. We will apply logistic regression models to estimate odds ratios for resistance in each quartile. To examine whether the relationship between adherence and resistance is quadratic, we will test a linearity of trends in odds ratios. If this linear trend is rejected, we will identify a quartile group that is associated with the highest odds of resistance. Potential covariates will be entered in regression models if found by univariate analysis to be associated ($p<0.2$) with resistance.

D.12.5. Hypotheses for Aim 3. We hypothesize that the total cost of delivering the CGT intervention will be lower than delivering the mDOT intervention, and that the incremental cost-effectiveness ratios for CGT v. TAU and mDOT v. TAU will each be less than \$100,000/QALY.

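### Aim 2 relates resistance found at any time to adherence at the final time point, so doses missed after on-treatment failure can look like a predictor of resistance

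*Combined protocol and SAP*

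**What the plan says.** **Exposure.** Section D.12.4 forms four groups from "quartiles of adherence measured at the final time point in the study" and estimates odds ratios for resistance by quartile. It does not name the final time point or the adherence measure. In Table 3, electronic adherence is read at weeks 4, 8 and 12 and self-report runs to week 24, while D.12.2 refers to six post-baseline points. For Aim 1, D.12.2 says that "adherence will be calculated as a single outcome for each subject, evaluated at the end of the study", which could mean either a last-interval or a cumulative value.

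**Adherence formula.** Section D.10.3 defines it as "Med-ic blister pack dose openings divided by total number of prescribed doses in time interval".

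**Outcome.** Section D.10.3 counts a telaprevir or sofosbuvir mutation "at any time point during the study, and the specific mutation did not exist at baseline". The ledipasvir wording is nearly the same: "during the study, and the specific mutation did not exist at baseline".

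**Testing.** Table 3 lists resistance tests at weeks 4, 8, 12 and 24 and at three follow-up visits. Section D.10.4 describes an assay "which is automatically run on any HCV viral load which is ≥ 2000 IU/ml", and adds: "For subjects who fail to achieve SVR, resistance testing will be performed on post-treatment specimen".

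**Shape.** Section D.12.3 expects a quadratic relation. Section D.12.4 examines it through a test of linear trend across the quartile odds ratios and, if linearity is rejected, picks out the quartile with the highest odds.

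**The concern.** An exposure should be measured before the outcome it is meant to explain. Here the outcome can be recorded from week 4 on, and the exposure is taken at the end. A participant whose virus breaks through at week 8 and who then loses heart and misses doses would be placed in the lowest quartile because of the resistance. Nothing in D.12.4 lags adherence, ends it at failure or discontinuation, or requires it to come first. The covariate rule (univariate p<0.2) does not touch timing.

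The adherence-resistance relation is one of the two parts of Aim 2 and is listed as an innovation in Section C. An artefact that loads events into the lowest quartile could create a trend where there is none. It could also hide an excess of resistance at intermediate adherence, and that is the kind of shape the quadratic hypothesis allows for.

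**Working it through.** **1. The plan's own figure.** D.13 expects resistance in 16% of each intensive arm and 30% of TAU. With 1:1:1 allocation, (16 + 16 + 30)/3 = 20.7%, which agrees with the roughly 20% in D.12.3. In 150 participants that is about 30 events (exact 95% CI for 30/150: 13.9% to 27.3%), or 30/4 = 7.5 per quartile if adherence has no effect. D.13 gives no power statement for this analysis.

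**2. Time order, case by case.**
- Resistance found at week 4 or 8: the weeks 8-12 adherence interval follows the outcome. A cumulative value to week 12 includes that interval too.
- Resistance first found after treatment: electronic monitoring covers only the first 12 weeks (D.10.4), so this adherence comes before the outcome and there is no problem.
- Resistance followed by doses that are no longer prescribed: those doses leave the denominator in D.10.3 if it follows the actual prescription. The final value is then missing or unaffected rather than low. The plan does not say which rule applies.

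**3. Size under no true effect.** Assumed, because the documents do not give them: three 4-week intervals, mean adherence about 83%, SD about 17%, and a share g of resistant participants whose final-interval adherence drops to between 0 and 30% of doses still counted as prescribed. From the documents: n = 150 and 20% resistance. Each run forms quartiles and applies a linear trend test at the two-sided 5% level.

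| g | Final interval: rejects | Final interval: median OR, lowest v. highest | Cumulative: rejects |
|---|---|---|---|
| 0% | 5% | 1.0 | 5% |
| 10% | 11% | 1.5 | 9% |
| 30% | 57% | 3.1 | 48% |
| 50% | 95% | 6.7 | 90% |

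Repeat runs differ by one to three percentage points. Adherence taken only before the change gives about 5% and an odds ratio of 1.0 at every g tested.

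**4. Hand check at g = 25%.** Mean simulated events per quartile, lowest to highest, are 12.3, 5.9, 5.8 and 5.9, with 150/4 = 37.5 participants in each. The odds are 12.3/25.2 = 0.488 in the lowest and 5.9/31.6 = 0.187 in the highest, so the ratio is 0.488/0.187 = 2.6. The false pattern is one raised quartile and three flat ones. It can be taken for a trend or for non-linearity, depending on how the shape test is carried out.

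**5. Fewer events.** With 100 participants and an assumed 5% resistance (5 events), the final-interval analysis rejects in about 5%, 11% and 31% of trials at g = 10%, 25% and 50%. The direction is the same, but there is little power for any conclusion.

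**6. Does an obvious repair work?** Ending the window at resistance for resistant participants only, with full follow-up for the rest, makes a new artefact if adherence drifts down. With an assumed fall of 8 points per 4 weeks and no true effect, the test rejects in 42% of trials with an odds ratio of 0.4. An early window common to everyone stays at about 5%.

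**The case against.** Four points can be made for the plan.

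- **The bias is not certain.** A reader might infer that the analysis will show a false association. The documents do not support that. The share g appears nowhere in them, and at g = 0 there is no bias. With 10% resistance and 5%, 10% or 15% of resistant participants affected, the test rejects in only 7%, 8% and 15% of trials, with odds ratios of 1.2, 1.4 and 1.6.
- **Few participants are involved.** It is tempting to say that exposure follows outcome for many of them. It can do so only within the roughly 20% expected to develop resistance, and among those only where it emerges on treatment before the last adherence interval. Testing of post-treatment specimens means that some cases will be relapses, where the order is correct.
- **A stop in treatment need not lower measured adherence.** If stopped doses no longer count as prescribed, the effect largely goes. With 10% resistance, mean adherence 80%, SD 16% and half of resistant participants stopping, rejection is 4% (final interval, stoppers missing) or 5% (cumulative), with an odds ratio of 1.0. This depends on a denominator rule that the plan leaves open.
- **Aim 2 is wider than this, and it speaks of associations.** The proportion with resistance and its exact interval are untouched, so it would be wrong to say that the whole aim fails. But calling the result an association does not rescue it: one produced by behaviour after the outcome says nothing about how adherence bears on resistance.

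The first three limit the size and the last the scope. None supplies the missing time order, and reading the final value as cumulative does not supply it either.

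**Conclusion.** The point holds as a risk built into the stated rule. For resistance that emerges on treatment before the last adherence interval, D.12.4 lets dosing after failure help to set the exposure, under either reading of the final time point. The distortion puts resistant participants in the lowest quartile. It ranges from nothing to an almost certain false trend over the range of g examined, and the documents do not allow a narrower statement. Even moderate shares matter, because moving a few of some 30 events is enough. The figures assume no true effect, 20% resistance, and missed doses that stay in the denominator. This should be corrected before analysis. It does not threaten the Aim 1 comparisons or the estimate of how often resistance occurs.

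**What to change.** In D.12.4, replace final-time-point adherence with electronic adherence over a window that precedes resistance and follows the same rule for everyone. Either version would do:

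1. Adherence over weeks 0-4 for all participants, with resistance first detected after week 4 as the outcome.
2. Cumulative adherence up to each resistance-test visit, comparing participants with newly detected resistance with those still free of it at that visit (for example, a discrete-time logistic model with time-updated adherence). Detection lags emergence, so repeat this with adherence lagged by one visit.

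Do not shorten the window for resistant participants only. State whether doses due after discontinuation count in the denominator, and name the visit meant by the final time point. Keep the final-time-point analysis as a sensitivity analysis.

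The cost is a short rewrite and somewhat more analysis. The first version uses less exposure information and leaves out resistance found at week 4. The second keeps more but needs a longitudinal data set. No new data are needed, because the monitors already record the time of each opening.

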For the analysis of repeatedly measured adherence (using 6 post-baseline time points and adherence as a continuous measure), we will apply mixed effects linear model to test if the 3 groups are significantly different. This model accounts for within-subject longitudinal outcome correlation by taking the subject-level intercept as random. The model will include potential confounding variables. If the omnibus equality test is rejected, we will conduct the 2 post-hoc pairwise tests described above. Concerning potential clustering effects in the CGT arm, we used pilot data (5 groups) to examine whether clustering influenced adherence. Between cluster variation was not significant, as tested by application of a random effects repeated-measure ANOVA model. Clustering in the GCT arm will be minimal, and we will not adjust for it in statistical or power analysis.

We will also apply mixed effects logistic regression to test the significance of mDOT and CGT on repeatedly-measured undetectable HCV VL throughout the intervention period, adjusting for substance use. Changes in illicit drug use will be analyzed using urine toxicology data from each visit, counting the “person-month” as a unit of analysis, and analyzing the proportion of person-months that are positive for use of illicit drugs using a chi-square analysis.

As secondary analyses, we will examine if mDOT and CGT effects, v. TAU, will be mediated by IMB components. We will assess IMB model mediators of adherence at baseline, and during the intervention, and will analyze changes in those variables from the baseline to the intervention period. The indirect effects of IMB mediators will be tested by assessing changes in coefficients of the intervention effect (mDOT or CGT) with and without IMB component(s) in mixed effects models. Confidence intervals of the mediated effects will be calculated by bootstrapping, and mediation assumed if confidence intervals do not include zero.

D.12.3. Hypotheses for Aim 2. We hypothesize that only a minority (~20%) of IDUs will develop resistance, and that the relationship between adherence and resistance will be quadratic.

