We will use the model to assess the cost-effectiveness of the 3 interventions: TAU, mDOT, and CGT. Primary outcomes will be projected life-expectancy, quality-adjusted life-expectancy (QALYs), lifetime costs, and incremental cost-effectiveness ratios measured in \$/QALY. We will forecast health and cost outcomes of each intervention for a hypothetical cohort of HCV patients using baseline study data on fibrosis, age, sex, and alcohol use, and study outcome data for each intervention including SVR, resistance, and retention in care. We will explore the potential impact of resistance mutations by varying the efficacy of subsequent HCV retreatment for patients with resistance who choose to be retreated. Lifetime costs will include the costs of the intervention received as well as projected future costs of HCV care depending on treatment effectiveness. Incremental cost effectiveness ratios will be calculated for TAU compared to no treatment and for mDOT and CGI compared to the next most expensive intervention, with costs and QALYs discounted at 3% annually according to standard practice.¹⁷³ The resulting ratios will be compared to a threshold of \$100,000 per QALY.¹⁷⁴⁻¹⁷⁵ To explore uncertainties in our results, we will perform one and 2-way sensitivity analyses on key input variables (e.g. probability of SVR and intervention cost) and probabilistic sensitivity analyses (PSAs) using second order Monte Carlo simulation on multiple variables.¹⁷⁶ For PSAs we will perform 1,000 simulations of a cohort of 100,000 individuals. The result will be a distribution of 1,000 model-based outcomes with a median and interquartile range that reflects underlying uncertainty in critical model parameters.

D.13 Power considerations Assuming a conservative attrition rate of 20%, 50 subjects per arm will begin the study, but 40 subjects per arm will complete it. For power calculations for repeatedly measured continuous or binary adherence outcomes, we will use the expected number of observations per subject. The power analysis is conducted based on the omnibus testing of equality across the three groups. It follows that at least one of the post-hoc pair-wise tests is powered to be rejected by this study design.

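### Aim 2 hypothesises a quadratic adherence-resistance relationship but tests it only as a departure from linearity across four quartiles, which loses power if the relationship is truly quadratic

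*Combined protocol and SAP*

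**What the plan says.** The Aim 2 hypotheses (section D.12.3) are that "only a minority (~20%) of IDUs will develop resistance" and that "the relationship between adherence and resistance will be quadratic".

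The analysis (section D.12.4) pools all 150 participants and forms "4 groups determined by quartiles of adherence measured at the final time point in the study". It continues: "We will apply logistic regression models to estimate odds ratios for resistance in each quartile". The quadratic hypothesis is then examined in one step, "we will test a linearity of trends in odds ratios", followed by: "If this linear trend is rejected, we will identify a quartile group that is associated with the highest odds of resistance".

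No squared term and no model with continuous adherence appears for Aim 2, although the mixed model in section D.12.2 already treats adherence as continuous for Aim 1. Section D.12.4 gives no significance level, degrees of freedom or quartile scores for this test. Section D.13 gives no power for it. The remark there about limited power for resistance concerns the comparison between arms.

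**The concern.** The hypothesis names a shape, and the test does not target that shape. With four groups, a departure-from-linearity test has 2 degrees of freedom and responds to any non-linear pattern. Treating everyone in a quartile as alike also removes the contrast in the tails, where much of the information on curvature lies. Rejection followed by naming the quartile with the highest odds would show some non-linearity and a highest group. A threshold or plateau could produce the same result.

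The adherence-resistance association is a main part of Aim 2 and is listed among the study's innovations in section C. At stake are a real quadratic relationship that goes undetected more often than it need, a non-significant result read as evidence against the hypothesis, and a significant one read as confirming a quadratic.

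**Working it through.** **No stated figure to reproduce.** The documents give no power, alpha or curvature for this test. A two-sided alpha of 0.05 is assumed throughout.

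**Inputs from the documents.** n=150 and about 20% resistance give 150 × 0.20 = 30 events, or 30/4 = 7.5 per quartile on average. The 20% attrition in section D.13 would leave 120 × 0.20 = 24 events, or 6 per quartile. Adherence means and SDs are 87% (SD 12) for mDOT and 77% (SD 20) for TAU (section D.13).

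**Step 1: information lost by grouping (large-sample approximation).** Efficiency is the share of the quadratic component's variance that survives when each value is replaced by its quartile mean.

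- Uniform adherence, rescaled to [−1, 1]: Var(x²) = 1/5 − 1/9 = 4/45. The mean of x² is 1/12 in the two inner quartiles and 7/12 in the two outer ones, so the between-quartile variance is ((7/12 − 1/12)/2)² = 1/16. Efficiency = (1/16)/(4/45) = 0.70.
- Normal adherence: Var(z²) = 2. The quartile cut is 0.6745, where the density is 0.3178. The inner mean is (0.5 − 2 × 0.6745 × 0.3178)/0.5 = 0.143 and the outer mean is 2 − 0.143 = 1.857. Between-quartile variance = ((1.857 − 0.143)/2)² = 0.734. Efficiency = 0.734/2 = 0.37.
- Skewed adherence (beta distributions, two-thirds with the mDOT mean and SD and one-third with the TAU values; using the mDOT values for CGT is an assumption): 0.37, found numerically.

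**Step 2: cost of the second degree of freedom.** For 80% power the noncentrality needed is 7.85 with 1 df and 9.63 with 2 df, a ratio of 9.63/7.85 = 1.23. Equal power therefore needs about 1.23/0.70 = 1.75 times the sample (uniform) or 1.23/0.37 = 3.3 times (normal or skewed).

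**Step 3: power by simulation.** The assumed truth is logit(p) = c − 0.5 × ((adherence − 80)/16)², with c set to give 20% resistance. The odds are then exp(−0.5) = 0.61 of the peak odds at 16 points from the peak, and exp(−2) = 0.14 at 32 points. Tests are likelihood-ratio tests, n=150.

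| Adherence distribution | Quartile departure test, 2 df | Squared term, 1 df | Loss (points) |
|---|---|---|---|
| Normal, mean 80%, SD 16%, no ceiling | 31% | 72% | 41 |
| Same, truncated at 100% | 20% | 42% | 22 |
| Skewed, as in step 1 | 18% | 55% | 37 |
| Uniform | 43% | 63% | 20 |

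The two normal rows show how much depends on handling of the 100% ceiling. The uniform row depends on the range assumed; a narrower range lowers both figures.

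**Step 4: sensitivity.**

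- Over a wider set of curvatures and peaks, with 20% resistance and n from 100 to 150, the quartile test lost about 15 to 70 points in every truly quadratic case. Replacing it by a 1-df quadratic contrast on quartile scores still lost about 11 to 68.
- Under a flat null (3,000 replicates) rejection was 6.3% and 5.3% for the quartile test and 5.4% and 6.7% for the squared term (uniform and skewed).
- Fewer events shrink the gap. For skewed adherence, peak at 80% and a curvature of 30 per unit of adherence squared (the step 3 curve is 0.5/0.16² = 19.5 on that scale), power was 31% v 80% at 20% resistance, 21% v 52% at 10% and 19% v 35% at 5%: losses of 49, 31 and 16 points.

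**The case against.** **The advantage assumes the parabola that the squared term fits.** This stands. With skewed adherence, a hump quadratic in adherence rank and centred at the median gave 68% (quartile) v 69% (squared term). Raising only the middle half gave 59% v 33%, and raising only the second quartile gave 65% v 45%. A raised band from 70% to 90% with normal adherence gave 81% v 71%. Quadratic may also be meant loosely, as highest in the middle, since the planned follow-up looks for a peak quartile. But the hypothesis as written is quadratic, and that is the alternative by which to judge its test.

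**A significant squared term does not show an inverted U either.** This stands too. Under a curve that is flat and then falls, with no peak, the squared term rejected in 38-61% of runs. The fix therefore needs a condition on the turning point.

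**Few events may limit any test.** Section D.9.6 puts SVR above 95% on the regimen that 100 of the 150 receive, and section D.10.4 ties resistance testing to viral load or treatment failure, so 20% may prove high. At an assumed 7.5 to 12 expected events, the unpenalised squared term had 24-51% power and rejected a true null in 8-11% of runs. Penalised likelihood is meant for this setting, but its performance here was not simulated.

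**A reader might infer that the plan uses a plain trend test, blind to an inverted U.** The documents do not support that. The test is introduced as an examination of whether the relationship is quadratic, and the next sentence, "If this linear trend is rejected, we will identify a quartile group that is associated with the highest odds of resistance", makes linearity the null hypothesis.

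**Conclusion.** The point holds as a mismatch between hypothesis and test. If the log-odds are truly quadratic in adherence, the planned quartile test has materially less power than a squared term in continuous adherence: about 18-43% against 42-72%, a loss of 20 to 41 points, under the step 3 assumptions. The direction held in every truly quadratic scenario tried. The size rests on assumed curvature, peak, adherence distribution and event rate, none of which the documents fix for this test.

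A reader might go further and infer that a true quadratic would usually be missed. The documents give no curvature from which to say so, and the quartile test reached 57-74% in several of the simulated quadratic scenarios. Nor does the squared term guarantee adequate power. The finding concerns a pooled, observational analysis with no claimed power, and leaves the randomised comparisons untouched.

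**What to change.** In section D.12.4:

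1. Make the test of the quadratic hypothesis the 1-df test of the squared term in a logistic model with centred continuous adherence and its square, using the same adherence measure. Fit by penalised likelihood because events are few, and state the significance level.
2. Report the turning point, mean adherence − b₁/(2b₂), where b₁ and b₂ are the linear and squared coefficients, with a confidence interval by a prespecified method. Claim an inverted U only if the squared term is significant and negative and that interval lies inside the observed adherence range.
3. Keep the quartile proportions and odds ratios as a description and a check on shape, not as the decisive test.

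The cost is analysis wording only, with no new data. The downside is that the squared term is less robust than the quartiles to humps that are not quadratic, which is why the quartile table should stay. Power remains limited if resistance events are few, so a non-significant result should not be reported as evidence against the hypothesis.
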